STUDY PROTOCOL: Lipids, inflammation, and cardiovascular risk in rheumatoid arthritis

NCT02714881

Protocol ID: 2016P000219

Last updated 5/11/2023

Objective

The objective of this study is to elucidate the relationship between inflammation and lipoprotein atherogenicity, and to determine the relative contribution of inflammation and lipids to cardiovascular (CV) risk in RA. Our central hypothesis is that inflammation and lipoprotein atherogenicity is tightly linked such that both factors are important to assess CV risk in RA. Further, we hypothesize that this relationship is obscured by a consideration of routine lipids alone.

Study population and design

The Lipids, Inflammation and CV Risk in RA (LiRA, ClinicalTrials.gov: NCT02714881) study conducted from 2016 to 2021, prospectively enrolled RA patients, age>35, with active RA with a plan to initiate tumor necrosis factor inhibitor (TNFi) therapy as directed by their treating rheumatologist. Exclusion criteria include prior cardiovascular disease, statin use, prednisone dose or equivalent >10mg, or biologic DMARD use in the past 24 weeks. All subjects underwent PET myocardial perfusion imaging (MPI) at baseline, were initiated on a TNFi, and returned for study visits at 6, 12 and 24 weeks, where a repeat PET MPI was performed. At each study visit, subjects had assessment of RA disease activity, current RA therapy, and screening for adverse events. Blood draws were also performed for measurements of fasting lipids, inflammatory markers and subclinical markers of myocardial injury.

A control group of healthy subjects with similar age and sex from our prior work using the same imaging protocol and quantitative analysis of myocardial perfusion PET images was also included to compare baseline imaging findings in the RA cohort. Inclusion criteria for this study were patients without a history or clinical evidence of CAD.

Assessment of myocardial blood flow and flow reserve

Myocardial blood flow was measured at rest and during maximal hyperemia using 15-20 mCi of ¹³N-ammonia as the flow tracer and a whole-body PET/CT scanner (Discovery RX or MI LightSpeed 64, GE Healthcare, Wakesha, WI). Low dose CT scans were used for attenuation correction and for semi-quantitative visual assessment of coronary artery calcification. Coronary artery calcium (CAC) was categorized as absent, mild (1-99), moderate (100-299), and severe (≥ 300). This semi-quantitative visual assessment correlates well with the Agatston score. Maximal hyperemia was achieved using regadenoson as per standard care. Patients were asked to refrain

from caffeinated products for 12 hours, theophylline-containing and arterial vasodilator medications the day of the study.

A semiquantitative 17-segment visual assessment using a standard 5-point scoring system was used to evaluate for myocardial ischemia and scar. Absolute MBF was computed from the rest and stress myocardial perfusion PET images using commercially available software (Corridor4DM; Ann Arbor, Michigan) and a two-compartment tracer kinetic model. All images were motion corrected and analyzed in a blinded fashion. Intrareader and inter-reader variability from our laboratory have previously been published. MFR was calculated as the ratio of stress over rest myocardial blood flow. All reported MBF and MFR values indicate global measure. MFR was calculated as the ratio of stress over rest myocardial blood flow. Rest MBF was also normalized by the rest rate-pressure product, an index of cardiac work, by dividing rest flow by the resting rate pressure product and multiplied by 10,000²². Corrected MFR was defined as stress MBF divided by corrected rest MBF. All reported MBF and MFR values indicate global measure. CMD was defined as a MFR <2.5, reflecting mild coronary microvascular dysfunction, based on prior work.

Effect of reducing inflammation on CMD, primary cohort

A TNFi, specifically certolizumab was used as the intervention to reduce inflammation. TNFi's are the most commonly used treatment after inadequate response to the first line therapy methotrexate for RA. Per our protocol, subjects were allowed to switch to other treatments if certolizumab was inadequate in controlling RA disease activity at the discretion of their treating rheumatologist with the overall goal to control inflammation.

The study was designed to enroll 75 subjects with an expectation anticipating 25% loss to follow-up with an anticipated of n=66 subjects completing the study. The study ultimately recruited 74 subjects with 66 subjects completing the study. As this study was initiated prior and enrolled through the COVID-19 pandemic, subjects' follow-up times extended beyond 24 weeks; this modification was approved by the Mass General Brigham Institutional Review Board. All patients were enrolled from rheumatology practices at Brigham and Women's Hospital, Brigham and Women's Faulkner Hospital, Massachusetts General Hospital, Boston, MA and Mount Auburn Hospital, Cambridge, MA. All PET MPI was performed at Brigham and Women's Hospital.

Study Outcomes and Measures

The primary outcome was the change in global MFR after 24 weeks of treatment starting with TNFi therapy. MFR, the ratio of peak vasodilator stress to rest MBF, represents the maximal ability to augment coronary flow and myocardial perfusion. The secondary outcome was change in hs-cTnT at baseline and 24 weeks. Inflammatory marker and hs-cTnT measurement was also available for baseline, week 6, 12 and 24 weeks.

Inflammatory biomarkers

Blood biomarkers were measured and broadly categorized into clinically measured acute phase reactants and inflammatory pathways implicated in RA or CVD. The acute phase reactants included: erythrocyte sedimentation rate (ESR) and high sensitivity C-reactive protein (hsCRP), measured using clinical assays. The remainder of the biomarkers were measured at Children's Hospital as previously described. Inflammatory pathways implicated in RA or CVD comprised of IL-1a, IL-1b, IL-6, and sTNFR2. Inflammatory biomarkers without clinical cut-off values were categorized into tertiles. Changes in biomarkers were also categorized into tertiles.

Clinical measurements

RA Disease Activity was assessed using the validated disease activity score (DAS)28-CRP with 3 components. DAS28-CRP3 incorporates the 28 tender and swollen joint count and hsCRP. We additionally calculated the clinical disease activity index (CDAI), which does not include hsCRP in the calculation.

Statistical Analysis

Means and standard deviations were used to describe most continuous variables, medians and IQRs were used to describe variables with non-normal distributions, and frequency and percent were used to describe categorical variables. Comparison p-values for outcome variables and other variables before and after TNFi therapy were computed using paired t-tests or the Wilcoxon signed rank test for non-normally distributed variables. Spearman's correlation was used to test the correlation between the log of baseline inflammatory markers and the primary outcome, MFR, and secondary outcome, hs-cTnT. As well, Spearman's correlation was used to test the relationship between change in inflammation and the primary and secondary outcomes. An exploratory subgroup analysis was also performed to test the correlation between change in inflammatory markers with change in hs-cTnT, among subjects with CMD (MFR<2.5) at baseline and 24 weeks. As measurements were available for inflammatory markers and hs-cTnT at

multiple time points, we additionally tested the association between the inflammatory markers with hs-cTnT over time.

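### CMD is defined by global MFR below 2.5 alone, so patients below the cut-off who have regional ischemia or scar on the study's own PET read are labelled microvascular

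*Combined protocol and SAP*

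**What the plan says.** The section *Assessment of myocardial blood flow and flow reserve* gives the whole rule: "CMD was defined as a MFR <2.5, reflecting mild coronary microvascular dysfunction, based on prior work". It also states that "MFR was calculated as the ratio of stress over rest myocardial blood flow" and that "All reported MBF and MFR values indicate global measure". The same section records a regional read of the scans: "A semiquantitative 17-segment visual assessment using a standard 5-point scoring system was used to evaluate for myocardial ischemia and scar".

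*Study Outcomes and Measures* makes the change in global MFR the primary outcome and says that MFR "represents the maximal ability to augment coronary flow and myocardial perfusion". The change in hs-cTnT is the secondary outcome.

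*Statistical Analysis* uses the CMD label once, in an exploratory correlation of change in inflammatory markers with change in hs-cTnT, "among subjects with CMD (MFR<2.5) at baseline and 24 weeks". No condition on the regional read is attached there either.

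Two sentences in *Study population and design* bear on who could have a defect. For the RA cohort: "Exclusion criteria include prior cardiovascular disease, statin use, prednisone dose or equivalent >10mg, or biologic DMARD use in the past 24 weeks". At the end of the control-group paragraph: "Inclusion criteria for this study were patients without a history or clinical evidence of CAD".

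**The concern.** By the plan's own description, MFR reflects the capacity to raise coronary flow as a whole. It does not separate the small vessels from the epicardial arteries. A low global value can come from diffusely reduced reserve, from a regional defect that pulls the average down, or from both. The 17-segment read is the item in this study that could help tell these apart, and the plan does not say how it is used.

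At stake is interpretation. The exploratory subgroup may mix two mechanisms under one name. The section describing the treated cohort is also headed *Effect of reducing inflammation on CMD, primary cohort*, which invites the reader to take a change in global MFR as a change in microvascular function.

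**Working it through.** The plan gives no figure to reproduce on this point: no count of abnormal reads and no size for the CMD subgroup. The check is one of text, followed by two illustrations on stated assumptions.

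**1. Is a normal regional read required anywhere?** The definition has one condition, global MFR below 2.5, and *Statistical Analysis* repeats it with that condition only. No section excludes patients with a defect, conditions on the read, or plans a sensitivity analysis without them.

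**2. Do the entry criteria close the gap?** The RA cohort exclusion concerns prior disease. It does not cover ischemia or scar first seen on the study PET. The sentence on absence of CAD follows the control-group text, so its scope is unclear. Even if it applies to the RA cohort, it refers to history and clinical evidence and does not mention the PET read.

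**3. Can a regional defect alone take global MFR below 2.5?** Treat the 17 segments as equal, and let *k* of them be abnormal. Let *r* be the MFR of the remaining segments and *d* the MFR of the abnormal ones. All values of *r* and *d* are assumptions.

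- Ischemia, equal rest flow: global MFR = [(17 − k)r + kd]/17. This is below 2.5 when k > 17(r − 2.5)/(r − d). For r = 3.0 and d = 1.5: 17 × 0.5/1.5 = 5.67, so 6 segments.
- Scar, rest flow halved: global MFR = [(17 − k)r + 0.5kd]/[(17 − k) + 0.5k]. This is below 2.5 when k > 17(r − 2.5)/[(r − 2.5) + 0.5(2.5 − d)]. For r = 3.0 and d = 1.0: 8.5/1.25 = 6.8, so 7 segments.

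Smallest number of abnormal segments that gives a global MFR below 2.5:

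| Remote MFR (r) | Ischemia, d = 1.0 / 1.5 / 2.0 | Scar, d = 1.0 / 1.5 |
|---|---|---|
| 2.6 | 2 / 2 / 3 | 3 / 3 |
| 2.8 | 3 / 4 / 7 | 5 / 7 |
| 3.0 | 5 / 6 / 9 | 7 / 9 |
| 3.5 | 7 / 9 / 12 | 10 / 12 |

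A defect can move a patient across the cut-off when reserve elsewhere is just above it. With good reserve elsewhere, the defect must be large.

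**4. How many could be affected?** Assume that 3% to 10% of the 66 completers have a defect: 0.03 × 66 ≈ 2 and 0.10 × 66 = 6.6 ≈ 7. Assume a CMD subgroup of 20 to 30.

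- If defects are no more common below 2.5 than above it, their share of the subgroup is the assumed 3% to 10%: 0.03 × 20 = 0.6 to 0.10 × 30 = 3 patients.
- If every patient with a defect falls in the subgroup, the share runs from 2/30 = 7% to 7/20 = 35%. This is an upper bound under these assumptions, not an estimate.
- If no read is abnormal, the share is zero.

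**The case against.** The best defence is that the label does little work. The cut-off enters one exploratory correlation, and no primary or secondary test depends on it. The cohort excludes prior cardiovascular disease, so large defects should be uncommon. The definition rests on prior work that cannot be seen here. The regional read may also have been meant for the planned comparison of baseline imaging findings or for descriptive tables. All of this stands as a limit on size. None of it supplies a rule for a patient who is below 2.5 and has an abnormal read.

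Four stronger readings are tempting, and the documents do not support them.

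- *Every patient with a regional defect is counted as CMD.* Only those whose global MFR is also below 2.5 are counted.
- *Patients with ischemia or scar have higher hs-cTnT and so drive the subgroup correlation.* The subgroup analysis correlates changes. A persistently higher level does not by itself produce a larger change, and if Spearman's method is used there too, ranks limit the pull of extreme values.
- *Up to a third of the subgroup is misclassified.* The 35% pairs the most assumed defects with the smallest assumed subgroup and places every defect inside it. A defect also does not make the label wrong if flow reserve is low elsewhere as well.
- *CMD should be redefined to require a normal read.* That would relabel as non-CMD a patient with diffusely low reserve and one small defect. Requiring it at 24 weeks would also select on a finding made after treatment began.

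**Conclusion.** The concern holds as a gap in definition and interpretation. As written, the rule labels a patient with global MFR below 2.5 and a regional defect as having microvascular dysfunction, although the study collected the read that would flag this. That much rests on the text alone.

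The size is unknown. It may be zero, and the illustrative shares above depend on an assumed defect rate, an assumed subgroup size and an assumption about where the defects fall. The direct effect is confined to the exploratory CMD-subgroup correlation. A reader might infer that the primary result is wrong; it is not affected numerically, because the change in global MFR does not use the cut-off. What is affected is the further step of calling that change an effect on CMD.

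**What to change.** Keep MFR below 2.5 as the main definition and add the following as a sensitivity analysis, labelled post hoc because the study ran from 2016 to 2021:

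1. State which 17-segment scores count as abnormal.
2. Report the number of subjects with an abnormal read at baseline and at 24 weeks, overall and among those with MFR below 2.5.
3. Repeat the CMD-subgroup correlation and the MFR-change analysis without subjects whose baseline read was abnormal. Report separately those abnormal only at 24 weeks.
4. Attribute findings to microvascular dysfunction only if they hold in step 3, judged by the estimate and its confidence interval, since a p-value will weaken with the smaller number alone.

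No new data are needed. The cost is precision. For the MFR change, with the SD unchanged, losing 2 to 7 of 66 widens the interval by a factor of √(66/64) = 1.02 to √(66/59) = 1.06. For the subgroup correlation, taking the standard error as proportional to 1/√(n − 3), going from 30 to 28 widens it by √(27/25) = 1.04. The extreme case of 20 to 13 widens it by √(17/10) = 1.30. If no read is abnormal, a single reported line settles the point.

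### The week-24 hs-cTnT change is tested only in patients with both values; a mixed model on all 74 would rest on a weaker missing-data assumption, with a small gain in precision

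*Combined protocol and SAP*

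**What the plan says.** All references are to the combined protocol and SAP.

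- Study Outcomes and Measures sets the secondary outcome: "The secondary outcome was change in hs-cTnT at baseline and 24 weeks". The next sentence shows that more data exist: "Inflammatory marker and hs-cTnT measurement was also available for baseline, week 6, 12 and 24 weeks".
- Statistical Analysis gives the test for before/after comparisons as "paired t-tests or the Wilcoxon signed rank test for non-normally distributed variables". It names no scale for hs-cTnT, no analysis set and no rule for missing values.
- The section on the effect of reducing inflammation (primary cohort) gives the numbers: "The study ultimately recruited 74 subjects with 66 subjects completing the study". It adds that follow-up ran past 24 weeks for some patients, without saying by how much.
- The week 6 and 12 values enter only an extra analysis in Statistical Analysis: "we additionally tested the association between the inflammatory markers with hs-cTnT over time". No method is named for it. Spearman correlation is named for other questions: baseline levels, change scores ("Spearman's correlation was used to test the relationship between change in inflammation and the primary and secondary outcomes") and a subgroup with microvascular dysfunction.

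**The concern.** A paired test can use only patients who have both values. A patient who gave samples at baseline, week 6 and week 12 and then left contributes nothing. The result describes the whole cohort only if those who left would have changed as the completers did, and the plan neither states that assumption nor checks it. This is the only named secondary outcome in a single-arm study, so no control arm offsets selective loss. The discarded values are already in hand, and a standard model can use them.

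The over-time association raises a different question. Four values from one patient are correlated, and the plan does not say how that is handled.

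**Working it through.** **Inputs.** From the documents: 74 recruited, 66 completed, four hs-cTnT visits. Not given: alpha, power, SD, within-patient correlation, the shape of the hs-cTnT distribution, when the dropouts left, and which samples they gave. Assumed: two-sided 5%, 80% power for a log-scale paired t-test in 66 as reference, and baseline-to-week-24 correlation ρ from 0.5 to 0.9. The plan has no power figure for hs-cTnT to reproduce.

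**1. Who is left out.** 74 − 66 = 8, and 8/74 = 10.8%. The count is *up to* 8, since a non-completer may still have given a week-24 sample.

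**2. Possible bias.** Let d_C and d_D be the mean changes in completers and dropouts. The cohort mean is (66·d_C + 8·d_D)/74, so the completer mean differs from it by (8/74)(d_C − d_D) = 0.108·(d_C − d_D). If dropouts did not change at all, the completer estimate would exceed the cohort value by 10.8% of d_C.

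**3. Precision gained from the dropouts.** With visit as a category and the covariance taken as known, the variance of the week-24 change relative to the paired analysis of 66 is

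ratio = R + (1 − R)·66/74, where R = Var(week 24 | earlier values) / Var(week 24 − baseline).

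- All 8 seen at weeks 0, 6 and 12, equal correlations: R = (1 + 3ρ)/[2(1 + 2ρ)]. At ρ = 0.5, R = 0.625 and the ratio is 0.625 + 0.375 × 0.892 = 0.959. At ρ = 0.9, R = 0.661 and the ratio is 0.963.
- Same visits, correlation decaying with the time gap: R = 0.5, ratio 0.5 + 0.5 × 0.892 = 0.946.
- Some of the 8 with fewer visits: 0.958 to 0.974.
- All 8 with baseline only: R = (1 + ρ)/2, ratio 0.973 at ρ = 0.5 and 0.995 at ρ = 0.9.

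With at least one post-baseline visit per dropout, the variance therefore falls by about 3% to 5%. With baseline only, it falls by 0.5% to 2.7%.

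**4. Power.** Φ[(1.960 + 0.842)/√ratio − 1.960] gives 82.0% at ratio 0.95 and 81.2% at 0.97, against 80%.

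**5. Completers alone.** With complete data, the categorical-visit model reproduces the visit means, so the ratio is exactly 1.00. Weeks 6 and 12 add nothing to the week-24 change in these 66 patients.

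**6. Scale.** Simulated power at n = 66, with the effect set so that the log-scale paired t-test has about 80%:

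| Assumed within-patient error | Log paired t | Raw Wilcoxon | Raw paired t |
|---|---|---|---|
| Normal on the log scale | 79–81% | 69–76% | 55–74% |
| Heavier tails on the log scale (t, 4 df) | 78–82% | 82–86% | 57–72% |

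The order of log t and Wilcoxon depends on an error shape that the documents do not describe.

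**7. Type I error of the planned change tests.** Under log-normal data, simulated rates were about 4% to 6% for the raw t-test and the raw Wilcoxon test, against a nominal 5%.

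**The case against.** The strongest reply is that little is lost. The outcome is defined by two visits, and using those two is not in itself inefficient: step 5 shows that weeks 6 and 12 add no precision in completers. The gain from the dropouts is one or two power points, and less if they left before week 6. Raw scale and completers are also inferences from silence and from the paired test, and the plan already allows for skewness by offering the Wilcoxon test. Preferring a ratio of geometric means is partly a choice of what to estimate. All of this stands, and it limits the size of the point. It does not answer the missing-data point: a paired test still excludes those without a week-24 value, and the plan gives no rule for them.

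Three stronger readings are tempting, and the documents do not support them.

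- *The planned tests have invalid error rates.* They do not (step 7).
- *The raw-scale tests clearly waste power.* The raw Wilcoxon test loses to the log t-test under log-normal error but overtakes it with heavier tails (step 6).
- *The over-time association has inflated false positives.* Spearman correlation applied to pooled visits, ignoring the patient, gave 10% to 25% simulated type I error under assumed correlations. But the plan never says it did this. It names Spearman for other questions and no method here. Silence shows missing detail, not an error.

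**Conclusion.** The point holds as a modest improvement to the secondary analysis. The paired test excludes up to 8 of 74 patients (10.8%) and relies on completers being representative. A mixed model on all 74 lets dropout depend on hs-cTnT values already observed. It also lowers the variance of the week-24 change by about 3% to 5%, assuming correlations of 0.5 to 0.9 and at least one post-baseline sample from each dropout. The main benefit is the weaker missing-data assumption, not power.

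The log scale gives a ratio that is easy to interpret. It adds power over the raw-scale tests only if hs-cTnT is roughly log-normal with multiplicative error. The over-time association needs its method stated. The primary MFR outcome is not affected.

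**What to change.** - **Secondary outcome.** Analyse log hs-cTnT from all 74 patients in a repeated-measures mixed model with visit as a categorical fixed effect, unstructured within-patient covariance and small-sample degrees of freedom (for example Kenward–Roger). Report the week-24/baseline geometric mean ratio with 95% CI. State how samples taken after 24 weeks are assigned to a visit. A random intercept alone is not a safe substitute: where patients truly differed in slope, it gave 9% to 13% simulated type I error for the week-24 change.
- **Sensitivity analysis.** Keep the planned paired test, and report how many hs-cTnT values exist at each visit.
- **Over-time association.** Name a separate mixed model with a patient-level effect, and enter each log marker as a patient mean and a within-patient deviation. Do not pool visits as if they were independent.

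**Cost.** SAP wording and standard software, with no new data. The plan is written in the past tense after enrolment, so the added model should be labelled as added at that stage. The downside is reliance on missing at random and approximate log-scale normality; the retained paired test shows whether the conclusion depends on the model.

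### The baseline marker correlations with MFR and hs-cTnT are not adjusted for age or sex, so a correlation arising from age (or sex) could be reported as an inflammation link

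*Combined protocol and SAP*

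**What the plan says.** All references are to the combined protocol and SAP.

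- **Statistical Analysis:** Spearman's method is used to test the "correlation between the log of baseline inflammatory markers and the primary outcome, MFR, and secondary outcome, hs-cTnT". No covariate, regression, partial correlation or stratification is named here or elsewhere.
- **Statistical Analysis, further analyses:** a similar "correlation was used to test the relationship between change in inflammation and the primary and secondary outcomes" and, for repeated measurements, "we additionally tested the association between the inflammatory markers with hs-cTnT over time". The latter has no stated model or covariates and does not cover MFR.
- **Study population and design:** the study "prospectively enrolled RA patients, age>35", with no upper age limit and no restriction by sex. Prior cardiovascular disease and statin use are excluded.
- **Same section:** age and sex are otherwise mentioned only for the external comparison group, "A control group of healthy subjects with similar age and sex from our prior work", which serves the baseline imaging comparison.
- **Study Outcomes and Measures:** the primary and secondary outcomes are defined as changes, in global MFR and in hs-cTnT.
- **Effect of reducing inflammation on CMD, primary cohort:** "The study ultimately recruited 74 subjects with 66 subjects completing the study".

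**The concern.** A two-variable correlation across patients of different ages mixes any direct marker-outcome relation with whatever age contributes to both. Suppose older patients tend to have higher inflammatory markers, lower MFR and higher hs-cTnT. The plain correlation would then be negative for MFR and positive for hs-cTnT even with no direct relation to inflammation. The same could happen through sex.

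The stated objective concerns how much inflammation and lipids each contribute to cardiovascular risk in RA. An unadjusted baseline correlation cannot separate a contribution of inflammation from one of age or sex. The imaging comparison with healthy controls uses a group of similar age and sex, but that does nothing for correlations computed inside the RA cohort.

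**Working it through.** **The plan's own figures.** The plan gives no significance level, power or target correlation for these analyses, so there is nothing of its own to reproduce. Its one sample-size calculation is separate ("designed to enroll 75 subjects with an expectation anticipating 25% loss to follow-up with an anticipated of n=66 subjects completing the study"): 75 × 0.75 = 56.25, not 66. That inconsistency does not bear on this point, which uses the actual numbers of 74 recruited and 66 completing.

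**Assumptions, none from the document.** Two-sided 5% test. Age, marker and outcome are normally distributed. The age-marker correlation is a and the age-outcome correlation is b (absolute values). There is no direct marker-outcome link. Sex is not modelled.

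**Step 1: critical value.** |rho| = t/√(df + t²), with df = n − 2. At n=74, t = 1.993 and df = 72, so 1.993/√(72 + 3.974) = 0.229. At n=66 it is 0.242.

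**Step 2: correlation produced by age alone.** The marker-outcome correlation is a·b. On the Spearman scale this is rho = (6/π)·arcsin(ab/2). For a = 0.4, b = 0.5: (6/π)·arcsin(0.10) = 0.191.

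**Step 3: chance of a significant result.** Use Fisher's z with standard error 1/√(n − 3) = 1/√71 = 0.1187. The critical value is atanh(0.229) = 0.2331. For a = 0.4, b = 0.5, atanh(0.191) = 0.194. The upper tail is P(Z > (0.2331 − 0.194)/0.1187) = P(Z > 0.33) = 0.37, and the lower tail is negligible.

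The same steps for other settings at n=74, beside simulated rates (20,000 to 40,000 data sets per setting in the main runs):

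| a / b | ab | Spearman rho from age alone | Rate by formula | Rate by simulation |
|---|---|---|---|---|
| 0 / 0.4 | 0 | 0 | 4.9% | 5.2% |
| 0.1 / 0.3 | 0.03 | 0.029 | 5.6% | 5.7% |
| 0.2 / 0.3 | 0.06 | 0.057 | 7.6% | 7.5% |
| 0.3 / 0.4 | 0.12 | 0.115 | 16.2% | 16.6% |
| 0.3 / 0.5 | 0.15 | 0.143 | 22.8% | 22.9% |
| 0.4 / 0.5 | 0.20 | 0.191 | 37.0% | 37.3% |

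At n=66 the last setting gives 33%.

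**Step 4: after adjustment.** The partial Spearman correlation is (r_xy − r_xc·r_yc)/√[(1 − r_xc²)(1 − r_yc²)], computed on ranks with c = age. In simulation over this range it is significant in 4.8% to 5.3% of studies, close to nominal.

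**Step 5: price of adjustment.** With age and sex as covariates, df falls from 72 to 70. The critical |rho| at n=74 becomes 1.994/√(70 + 3.978) = 0.232, against 0.229.

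**The case against.** **The harm is not shown.** Confounding needs age (or sex) to be related to both the marker and the outcome, and the document gives neither correlation. If age is unrelated to the marker, the plain test keeps its 5% level, and at 0.1/0.3 the excess is under one percentage point. This stands, which is why the range starts at no harm.

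**The outcome in that sentence is ambiguous.** The outcomes are defined elsewhere as changes. If the baseline markers were correlated with changes, the cross-sectional age argument would not apply directly. This also stands. Baseline levels are a plausible reading, but the plan has to confirm it.

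**These are supporting correlations, not causal claims.** In part. The primary result is a paired before-after comparison, which this does not touch. But the section says the correlations were used to test, and it labels only the CMD subgroup analysis exploratory.

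Stronger readings that a reader might infer, and that the document does not support:

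- *That the bias favours the study's hypothesis.* The stated hypotheses link inflammation with lipoprotein atherogenicity and hold both important for assessing CV risk. No direction is stated for a marker against MFR or hs-cTnT.
- *That choosing controls of similar age and sex concedes confounding here.* It suggests relevance to imaging. It says nothing about hs-cTnT, or about age or sex being related to the markers.
- *That the risk over all six named markers measures this problem.* Assuming an inter-marker correlation of 0.3, the chance of at least one false link with hs-cTnT is about 25% even after adjustment. That part is multiplicity. The excess above it requires assuming that all six markers share one age correlation.
- *That the size is known for sex.* Sex could add to the effect of age or offset it.

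**Conclusion.** The concern holds in a limited form. The baseline correlations are specified without adjustment, age varies freely above 35 in the cohort, and no other part of the plan controls for age or sex in these analyses. A correlation due to age or sex could therefore be reported as an inflammation link. The document does not show that this has happened.

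For age, the false-positive rate per test at n=74 runs from about 5% to about 37%, against about 5% after adjustment. That range rests wholly on assumed correlations (0/0.4 to 0.4/0.5), a two-sided 5% test, and reading MFR and hs-cTnT as baseline levels. Because the remedy costs so little, the improvement is worth making even though the size is uncertain.

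**What to change.** In the Statistical Analysis section:

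1. State whether the baseline markers are correlated with baseline levels of MFR and hs-cTnT or with their changes.
2. If baseline levels are meant, add a partial Spearman correlation (on ranks) of each baseline marker with baseline MFR and with baseline hs-cTnT, adjusted for age and sex.
3. Report it beside the unadjusted rho, and label the unadjusted rho descriptive.
4. Rest any statement of an association independent of age and sex on the adjusted value.
5. The study ran from 2016 to 2021 and the document was last updated in 2023. If the unadjusted results are already known, label the adjusted analysis a post hoc re-analysis.

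Cost: a short wording change, a re-run using age and sex, which should already be held, and two degrees of freedom. Some correlations may shrink. Confounding by other factors, and multiplicity across markers, would remain.
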